### **8.1.1. Trial Period**

Estimated date first subject screened: Q1 2018

Estimated date last subject completed (24 weeks treatment period): Q4 2019

Estimated date last subject completed (follow-up period): Q1 2020

The duration of trial participation for each subject is approximately 60 to 70 weeks:

- Screening period for the subjects is up to 10 weeks
- Treatment period up to 48 weeks (+/- 7 days)
- Follow-up for 12 weeks (+/- 7 days)

### **8.1.2. End of Trial**

The end of the trial is defined as the last subject's last visit (LSLV).

### **8.1.3. Trial completion**

Trial completion is defined as the date of the Clinical Trial Report (CTR).

## **8.2. Number of Subjects**

It is planned that 30 subjects will be enrolled. No formal sample size calculation was done as this is an initial pilot study.

## **8.3. Treatment Assignment**

At Screening (Visit 1), the subject will be assigned a site-specific subject number that will continue to be the unique identifier throughout the trial. The subject number will be generated automatically by the electronic data capture system used in the trial. The subject number will be in the following format XX-YYY. The letter XX is the site number and YYY the consecutive subject number starting at 101 at each site.

At the Baseline visit, all subjects found to be eligible according to the inclusion/exclusion criteria will be classified into the following treatment groups by a central electronic data capture system:

- Group 1: Subjects who remain sputum culture positive while currently on a multidrug NTM guideline based antimycobacterial regimen, which has been ongoing for at least 6 months prior to the Baseline Visit.
- Group 2: Subjects who remain sputum culture positive but have either stopped a multidrug NTM guideline based antimycobacterial regimen at least 28 days prior to Screening due to lack of response or intolerance, or never started such treatment.

Patients successfully assigned to a subgroup will then start treatment with open-label molgramostim nebulizer solution.

#### **8.4. Dose Adjustment Criteria**

A data review was conducted by a safety review committee comprised of the lead investigators and sponsor representatives after the first 6 subjects had completed 12 weeks of treatment. If safety concerns or poor tolerability were identified in this review, the review committee might decide on less frequent dosing for subsequent subjects in the study. The review concluded that no dose adjustment was required. Any changes to the conduct of the study such as change of dose regimen will be documented in a protocol amendment.

Subjects who experience poor tolerability to treatment (i.e. unacceptable respiratory or gastrointestinal symptoms, the nature of which may be assumed to be reversible) may reduce the dose. Prior to dose reduction, the Sponsor medical monitor must be consulted.

##### **8.4.1. Safety Criteria for Adjustment or Stopping Doses**

No prespecified safety criteria have been defined for the safety review committee.

##### **8.4.2. Pharmacokinetic Criteria for Adjustment or Stopping Doses**

Not applicable.

#### **8.5. Criteria for Study Termination**

The investigator or the sponsor may terminate this trial prematurely for any reasonable cause. The Independent Ethics Committees (IECs)/Institutional Review Boards (IRBs) and Competent Authorities (CAs) should be informed promptly.

Conditions that may warrant termination include, but are not limited to:

- The discovery of an unexpected, significant, or unacceptable risk to the subjects in the trial, or potential trial subjects
- A decision on the part of the sponsor to suspend or discontinue development of the IMP

If the CA obtains information that raises doubts about the safety or scientific validity of the clinical trial, the CA can suspend or prohibit the trial. Before the CA reaches its decision, it shall, except where there is imminent risk, ask the sponsor and/or the investigator for their opinion, to be delivered within one week (Directive 2001/20/EC, Article 12, Section 1).

If the trial is prematurely terminated or suspended for any reason, the investigator/institution should promptly inform the trial subjects and should assure appropriate therapy and follow-up for the subjects.

## 9. SELECTION AND WITHDRAWAL OF SUBJECTS

Subject fulfilling all inclusion and none of the exclusion criteria can be enrolled in the trial. An enrolled subject is defined as a subject receiving treatment with the trial IMP.

### 9.1. Subject Inclusion Criteria

1. History of chronic pulmonary infection with MAC or *M. abscessus* (defined as at least 2 documented positive sputum cultures in the prior 2 years, of which at least one was obtained in the 6 months prior to Screening).
2. Subject fulfills one of the following criteria:
  - Subjects who remain sputum culture positive while currently on a multidrug NTM guideline based antimycobacterial regimen, which has been ongoing for at least 6 months prior to the Baseline Visit
  - Subjects who remain sputum culture positive but have either stopped a multidrug NTM guideline based antimycobacterial regimen at least 28 days prior to Screening due to lack of response or intolerance, or never started such treatment.
3. Ability to produce at least 2 mL of sputum or be willing to undergo an induction that produces at least 2 mL of sputum for clinical evaluation.
4. Female or male  $\geq 18$  years of age.
5. Females who have been post-menopausal for more than 1 year or females of childbearing potential after a confirmed menstrual period using a highly efficient method of contraception (i.e. a method with less than 1% failure rate such as combined hormonal contraception, progesterone-only hormonal contraception, intrauterine device, intrauterine hormone-releasing system, bilateral tubal occlusion, vasectomized partner, sexual abstinence), during and until thirty (30) days after last dose of trial treatment. Females of childbearing potential must have a negative serum pregnancy test at Screening (Visit 1) and a negative urine pregnancy test at dosing at Baseline (Visit 2) and must not be lactating.
6. Males agreeing to use condoms during and until thirty (30) days after last dose of medication, or males having a female partner who is using adequate contraception as described above.
7. Willing and able to provide signed informed consent.

---

 Sexual abstinence is considered a highly effective method only if defined as refraining from heterosexual intercourse during the entire period of risk associated with the study treatments. The reliability of sexual abstinence needs to be evaluated in relation to the duration of the clinical trial and the preferred and usual lifestyle of the subject.

8. Willing and able to comply with scheduled visits, treatment plan, laboratory tests, and other trial procedures specified in the protocol as judged by the investigator

## **9.2. Subject Exclusion Criteria**

1. Subjects diagnosed with cystic fibrosis.
2. Prior therapy with inhaled or systemic GM-CSF.
3. Subjects with hemoptysis of  $\geq 60$  mL in a 24 hour period within 4 weeks prior to Screening.
4. Concurrent disease with a life expectancy of less than 6 months.
5. History of, or present, myeloproliferative disease, leukemia or other hematological malignancy.
6. Active pulmonary malignancy (primary or metastatic); or any malignancy requiring chemotherapy or radiation therapy within one year prior to Screening or anticipated during the study period.
7. Active allergic bronchopulmonary mycosis or connective tissue disease, inflammatory bowel disease or other autoimmune disorder requiring therapy associated with significant immunosuppression, such as systemic corticosteroids at a dose equivalent of 10 mg/day or more of prednisolone, within 3 months prior to Screening or anticipated during the study period.
8. Pulmonary tuberculosis requiring treatment or treated within 2 years prior to Screening.
9. HIV infection or other disease associated with significant immunodeficiency.
10. History of lung transplantation.
11. Any change in chronic NTM multi-drug antimycobacterial regimen within 28 days prior to Screening.
12. Treatment with any investigational medicinal product within 3 months of Screening.
13. Previous experience of severe and unexplained side-effects during aerosol delivery of any kind of medicinal product
14. Any other serious medical condition which in the opinion of the investigator would make the subject unsuitable for the trial.

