| Eligibility criteria                   | X         | X                 |                  |                  |                  |                   |                   |                   |                   |                   |                   |                   |                   |                   |                   |                                |
| Demographics and body measurements     | X         |                   |                  |                  |                  |                   |                   |                   |                   |                   |                   |                   |                   |                   |                   |                                |
| Medical history                        | X         |                   |                  |                  |                  |                   |                   |                   |                   |                   |                   |                   |                   |                   |                   |                                |
| Body weight                            |           | X                 | X                | X                | X                | X                 | X                 | X                 |                   | X                 |                   | X                 |                   | X                 | X                 | (X)                            |
| Prior and Concomitant medication       | X         | X                 | X                | X                | X                | X                 | X                 | X                 | X                 | X                 | X                 | X                 | X                 | X                 | X                 | X                              |
| Pregnancy test and contraceptive check | X         | X                 | X                | X                | X                | X                 | X                 | X                 | (X)               | X                 | (X)               | X                 | (X)               | X                 | X                 | (X)                            |

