## 8. INVESTIGATIONAL PLAN

### 8.1. Overall Trial Design

This is an open-label, non-controlled, multicenter, pilot clinical trial of inhaled molgramostim in subjects with persistent pulmonary NTM infection.

The primary objective is to investigate efficacy of inhaled molgramostim on NTM sputum culture conversion to negative. The primary endpoint is sputum culture conversion defined as at least three consecutive negative sputum samples during the treatment period.

Secondary objectives are to investigate the efficacy of inhaled molgramostim on NTM sputum smear conversion to negative, on reduction of NTM bacterial load in sputum and on Patient Reported Outcomes, exercise capacity as well as evaluation of the safety of inhaled molgramostim in these subjects.

Secondary efficacy endpoints and the safety endpoints are detailed in Section 7.3.

The study will comprise a Screening Visit, Baseline Visit, a 48-week treatment period and a 12-week follow up period. The Screening Visit (Visit 1) will be conducted up to 10 weeks prior to the Baseline Visit (Visit 2) to determine eligibility. Adult subjects with a history of chronic NTM infection with at least 2 positive cultures in the prior two years, of which at least one is within the last 6 months prior to Screening, will be considered for enrollment. Subjects should provide a positive NTM sputum culture at Screening to be eligible.

Two subgroups of subjects will be recruited:

- Group 1: Subjects who remain sputum culture positive while currently on a multidrug NTM guideline based antimycobacterial regimen, which has been ongoing for at least 6 months prior to the Baseline Visit.
- Group 2: Subjects who remain sputum culture positive but have either stopped a multidrug NTM guideline based antimycobacterial regimen at least 28 days prior to Screening due to lack of response or intolerance, or never started such treatment.

The study will include 30 subjects.

The treatment period will consist of 14 trial visits (Screening, Baseline, and at Weeks 4, 8, 12, 16, 20, 24, 28, 32, 36, 40, 44, and 48; Visits 1-14) and a follow-up visit (Visit 15) 12 weeks after end of treatment. The visits at Weeks 28, 36 and 44 (Visits 9, 11 and 13) will include a telephone contact, all other visits will include a clinic visit.

At the Baseline Visit (Visit 2), eligible subjects will start treatment with inhaled molgramostim administered via the PARI eFlow nebulizer.

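### Exclusion 11 stops at Screening although first dose may follow up to 10 weeks later, so a Group 1 regimen modified in between stays eligible and a resulting conversion counts for molgramostim

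*Protocol*

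**What the plan says.** **Stability rule.** Protocol 9.2, exclusion 11: "Any change in chronic NTM multi-drug antimycobacterial regimen within 28 days prior to Screening".

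**Time to first dose.** Protocol 8.1: "The Screening Visit (Visit 1) will be conducted up to 10 weeks prior to the Baseline Visit (Visit 2) to determine eligibility". First dose is given at Baseline (Protocol 11.5).

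**Group 1 entry.** Protocol 9.1 requires a guideline-based multidrug regimen "which has been ongoing for at least 6 months prior to the Baseline Visit".

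**Checks.** The "Eligibility criteria" row of Protocol Table 1 is marked at both Screening and Baseline. The culture that counts for entry is the Screening culture: "Subjects should provide a positive NTM sputum culture at Screening to be eligible".

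**Medication changes.** Protocol 12.3 asks that changes be kept to a minimum, allows them at the investigator's discretion, and has them recorded with reasons.

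**Analysis.** In SAP 3.3.3 the sputum baseline combines Screening and Baseline, and one positive sample makes it positive. SAP 4.1.1 analyses everyone enrolled. SAP 9.2.1 defines conversion by negative samples at three consecutive visits, with nothing on background therapy. The only sensitivity analysis in SAP 9.3.1.2 concerns how many samples are available per visit. SAP 10.4 flags antimycobacterials and regimen changes in the prior and concomitant listings and adds a table of concomitant antimycobacterials.

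**The concern.** The trial has no control arm. Whether a conversion can be credited to molgramostim rests largely on the background regimen not having just changed. Exclusion 11 is the only eligibility rule that addresses such a change, and it leaves out the weeks closest to first dose.

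The gap is also a natural time for a change. Every eligible subject has a positive Screening culture, and that result may prompt the treating physician to adjust the regimen. This is an inference; the documents give no frequency.

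The pooled baseline adds to the problem. A subject whose regimen was modified after Screening and whose Baseline samples were already negative is still baseline positive, and can become a converter by staying negative at three consecutive visits on treatment.

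**Working it through.** No figure in the plan needs reproducing. Protocol 8.2 and SAP 2.3 state that no formal sample size calculation was done.

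**1. Days covered and not covered**

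Inputs: a 28-day look-back (exclusion 11) and a maximum of 10 weeks from Screening to Baseline (Protocol 8.1; Table 1 writes less than 10 weeks, a difference of one day).

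- Uncovered: 10 × 7 = 70 days, which is 70/28 = 2.5 times the look-back.
- Start of the look-back to the latest first dose: 28 + 70 = 98 days, of which 70/98 = 71% carry no stability rule.
- Window from 28 days before Screening through first dose: 98 days covered, 0 uncovered.
- Window moved to 28 days before Baseline only: 70 − 28 = 42 days after Screening still uncovered.

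**2. Does another provision close the gap?**

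- *Visit 2 eligibility check.* It re-reads a criterion worded relative to Screening. A change made after Screening does not meet that wording on any date.
- *Six-month rule for Group 1.* It sets how long the regimen has run. If it meant unchanged for six months, exclusion 11 would be redundant for Group 1.
- *Protocol 12.3.* A request to minimise changes, with discretion to make them, is not an eligibility rule.
- *Exclusions 6 and 7.* These reach past Screening because they also cover what is anticipated during the study. Exclusion 11 has no such words.

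**3. Effect of one subject on the primary result**

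Inputs: 30 subjects and a 30% mark (Protocol 13; SAP 9.3.1.1). The split between groups is not given, so 15 per group is an assumption. The subject is taken to convert only because of the regimen change. One conversion adds 1/30 = 3.3 points or 1/15 = 6.7 points. Exact (Clopper-Pearson) 95% intervals:

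| Subjects | Without | With |
|---|---|---|
| 30 | 8/30 = 26.7% (12.3 to 45.9) | 9/30 = 30.0% (14.7 to 49.4) |
| 15 (assumed) | 4/15 = 26.7% (7.8 to 55.1) | 5/15 = 33.3% (11.8 to 61.6) |

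A single subject can carry the point estimate to or over 30%. The intervals are wide and barely move.

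**4. Chance of observing at least 30%**

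The true molgramostim rates of 10% and 20% are assumptions. One affected subject replaces one ordinary subject and converts with probability 0.5 or 1.0.

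| Subjects, true rate | None affected | One, 0.5 | One, 1.0 |
|---|---|---|---|
| 15, 20% | 0.16 | 0.22 | 0.30 |
| 30, 20% | 0.13 | 0.16 | 0.21 |
| 15, 10% | 0.01 | 0.03 | 0.04 |
| 30, 10% | 0.002 | 0.004 | 0.006 |

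These figures show how sensitive the result is to one subject. They do not estimate the bias.

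**The case against.** The case for leaving the criterion alone has weight.

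- *Purpose.* No section states why exclusion 11 exists, and ending it at Screening matches the culture that decides entry. It also allows a change 29 days before Screening, so it never guaranteed a long-stable background. This stands. Protecting attribution is an inference, and it is too strong to say that the gap defeats the rule.
- *Expected effect.* Protocol 6.2 expects no response to further NTM treatment in this population. That is an expectation, not data. It also sits uneasily with having exclusion 11 at all, and with Protocol 8.1 allowing antimycobacterials to be added or increased as rescue.
- *Visibility.* Changes are recorded and listed with reasons, so affected subjects can be found. This stands, but no planned analysis uses the information.
- *Rescue.* Antimycobacterial changes during 48 weeks of treatment are open and unadjusted. This stands and limits the gain. It is a separate attribution problem that closing the gap does not solve.

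A reader might also infer more than the text supports:

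- *Exclusion 12 has the same gap.* It reads "Treatment with any investigational medicinal product within 3 months of Screening". The word *of*, where other criteria say *prior to*, may cover both sides of Screening. It is ambiguous, not clearly open.
- *Group 2 subjects who restart treatment stay eligible.* Those who "have either stopped a multidrug NTM guideline based antimycobacterial regimen at least 28 days prior to Screening" and then resume would still fit the literal words. But groups are assigned at Baseline, and Protocol 6.2 describes Group 2 as untreated subjects. A never-treated subject who starts in the gap fails both limbs of inclusion 2.
- *A Group 1 subject could begin an entirely new regimen in the gap.* The six-month rule, anchored at Baseline, excludes that. Only modification of a continuing regimen gets through.
- *Exclusion 3 is another open washout.* It concerns hemoptysis of 60 or more "mL in a 24 hour period within 4 weeks prior to Screening", which is a clinical safety criterion. All that can be said is that its window also ends at Screening.

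**Conclusion.** The point holds for Group 1 subjects whose continuing regimen is modified between Screening and first dose. They are eligible as the protocol is written, and the primary analysis credits any resulting conversion to molgramostim. The uncovered period is up to 70 days. The effect is 3.3 points per such converter with 30 subjects, or 6.7 points with an assumed 15 per group, which is enough to move a point estimate across 30%.

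This rests on the literal wording of exclusion 11, on reading the six-month rule as one of duration, and on the conversion being due to the change. The number of such subjects is unknown and may be zero, so the documents do not show that the reported rate will be biased. It is a modest weakness in a descriptive pilot, worth correcting because correction is cheap.

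**What to change.** **Protocol 9.2, exclusion 11.** Extend the window, keeping the 28-day threshold, for example: *any change in the chronic NTM antimycobacterial regimen from 28 days before Screening through first dose.* Moving the anchor to Baseline alone is not enough. This says nothing about when a regimen should be changed; a subject whose regimen is changed fails screening or is re-screened.

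**SAP 9.3.1.2, for subjects already enrolled.** Add a sensitivity analysis of the conversion rate, with exact 95% intervals by group and overall, excluding subjects whose antimycobacterial treatment changed between Screening and first dose. Identify them from the changes recorded under Protocol 12.3 and flagged under SAP 10.4. In the examples above, removing one affected converter turns 9/30 = 30.0% into 8/29 = 27.6%, and 5/15 = 33.3% into 4/14 = 28.6%. If no subject is affected, one sentence in the report is enough.

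**Exclusion 3.** The sponsor should reconcile its Screening-anchored window with the later first dose. How to do so is a clinical decision.

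**Cost.** A wording amendment, one table from data already collected, and a few extra screen failures or re-screens. On-treatment rescue needs its own analysis rule.

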### **9.3. Subject Withdrawal Criteria**

#### **9.3.1. Discontinuation from Trial Treatment**

Subjects may be discontinued from treatment and assessments at any time, if deemed necessary by the investigator.

Potential reasons for discontinuation of treatment are:

- Lack of efficacy/worsening of disease
- Unacceptable AE
- Serious hypersensitivity reaction
- Pregnancy

Those who discontinue treatment will not automatically be withdrawn from the trial but will be encouraged to continue to follow the same visit schedule. For example: if treatment is discontinued at Week 4 (Visit 3) the subject will be encouraged to attend the remaining visits.

The reason and date the subject is discontinued from treatment will be documented in the electronic case report form (eCRF).

#### **9.3.2. Withdrawal from the Trial**

Subjects are free to discontinue their participation in the trial at any time. Withdrawal from the trial will not affect or prejudice the subject's further care or treatment. Potential reasons for withdrawal of subjects from the trial are:

- Screening failure
- The decision of a subject to withdraw from the trial (including if the subject withdraws informed consent)
- Unacceptable treatment response
- Unacceptable adverse event
- Subject is lost to Follow-up
- Other reason(s) (e.g incorrect enrollment)

The reason and date the subject is withdrawn from the trial will be documented in the eCRF (e.g. lost to follow-up, consent withdrawn, incorrect enrolment, AEs, etc.). If a subject is withdrawn from the trial, the investigator should attempt to complete all required trial assessments (such as those at Week 48 if withdrawn during the treatment period).

All AEs should be followed-up according to Section [12.15](#).

If a subject is withdrawn from the trial, all data collected until the time of withdrawal will be used in the data presentations unless consent to use the data was withdrawn by the subject.

